THE STUDY PROTOCOL

date: 2024-07-16

PROTOCOL ID: UMED-RNN/223/20/KE

Title: Evaluation of the Effectiveness and Safety of Blue Light Emitted by LED Lamps Using the PHLECS Device in the Treatment of Inflammatory Skin Diseases

THE STUDY PROTOCOL

date: 2024-07-16

ID: UMED-RNN/223/20/KE

Title: Evaluation of the Effectiveness and Safety of Blue Light Emitted by LED Lamps Using the PHLECS Device in the Treatment of Inflammatory Skin Diseases

- The study involves four groups of patients (patients with psoriasis, atopic dermatitis, eczema and chronic pruritus)
- The study is scheduled for a maximum of 60 irradiations of blue light (maximum 3 cycles of 20 irradiations each). Phototherapeutic light will be administered for 15 minutes to each side of the body of the patient (30 minutes in total), 3-5 times per week.
- Device

Full Body Blue GEN 1.0 device (built by PHLECS B.V., Phlecs, [name]) with European Community (EC) Certificate (number 2238613CE01) is used in the study. The device provides phototherapeutic light through light panel with treatment Light Emitting Diodes - LEDs (wavelength 453 nm, irradiance 40mW/cm²; dose 36J for 15min treatment) to one side of the body of the patient who is lying flat on an examination bed

- After consent to participate in this study, the observation period will begin and will last a maximum of 12 weeks

1. Day 0 - screening and inclusion, during which the following will be assessed:

- skin examination (including photo documentation), assessing skin phototype according to Fitzpatrick's scale
- detailed medical history collection
- quality of life assessment – DLQI
- Additionally, appropriate scales will be used depending on the disease:
PASI, PGA, VAS, 10-item Pruritus Severity Scale - psoriasis vulgaris
IGA, VAS, 10-item Pruritus Severity Scale - eczema
SCORAD, EASI, VAS, 10-item Pruritus Severity Scale - atopic dermatitis
VAS, 10-item Pruritus Severity Scale – chronic pruritus
- an interview will be made regarding comorbidities and the treatment used
- blood samples collection
- Optionally, only in patients who give additional consent a skin biopsy will be taken to evaluate the mechanism of action of blue light.

2. visit 1 – first full-body blue irradiation

3. Visit 2 – evaluation of the effectiveness and safety after 10 sessions of blue light phototherapy, Blood sample collection

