4. Visit 3 – evaluation of the effectiveness and safety after 20 sessions of blue light phototherapy (= after the first cycle of irradiation), Blood sample collection
5. Visit 4 – evaluation of the effectiveness and safety after 30 sessions of blue light phototherapy, Blood sample collection
6. Visit 5 – evaluation of the effectiveness and safety after 40 sessions of blue light phototherapy (= after the second cycle of irradiation), Blood sample collection
7. Visit 6 – evaluation of the effectiveness and safety after 50 sessions of blue light phototherapy, Blood sample collection
8. Visit 7 - end of treatment visit - after 60 sessions of blue light phototherapy (= after the third radiation cycle), during which we will re-evaluate the condition of the skin, quality of life, safety of the device used and blood samples will be taken. Optionally, with additional consent, a skin biopsy will be taken. If, for any reason, the study is terminated earlier or if the skin lesions have completely disappeared before 60 irradiations - the end of treatment visit will take place earlier
9. Visit 8 – assessment of the clinical condition 4 weeks after the cessation of therapy

During blue light therapy, follow-up visits will be performed to assess the safety and effectiveness of the device. At the last control visit (end of treatment visit) the same parameters will be assessed as during the first one. In the case of remission of skin lesions earlier than envisaged in the study protocol, the end of treatment visit will take place earlier. Photographic documentation will be carried out at each visit. During the treatment patients were allowed to use emollients.

Inclusion criteria:

1. Informed consent to participate in a medical experiment
2. Age over 8 years of age
3. Diagnosis of psoriasis / eczema / atopic dermatitis
4. Chronic pruritus (lasting more than 6 weeks)
5. Good general health (no history of other clinically significant diseases according to the doctor's assessment)
6. A patient who is able to understand the information related to the experiment, meet the requirements contained in the protocol of the experiment, who undertakes to strictly follow medical recommendations and appear on time for visits.

Exclusion criteria:

1. Patients with known hypersensitivity to ultraviolet or blue radiation
2. Age under 8 years of age
3. Women who are pregnant, breastfeeding or planning to become pregnant during the experiment

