4. Patients who participated in another experiment / clinical trial within 30 days prior to inclusion in the experiment
5. Patients unwilling or unable to respect the requirements of the experiment
6. Patients with skin diseases other than inflammatory skin diseases or chronic pruritus
7. Planned hospitalizations or surgical procedures during the medical experiment
8. Patients using medications with proven phototoxic effect
9. Diastolic blood pressure > 95mmHg and < 65mmHg
10. Patients with congenital or acquired immune disorders

11. Patients with a history or at the time of the examination diagnosed with a malignant skin cancer, severe actinic keratosis or dysplastic moles
12. Patients diagnosed with genophotodermatoses, increasing the risk of skin cancers, including xeroderma pigmentosum, Cockayne's syndrome, Bloom's syndrome)
13. Patients addicted to alcohol / drugs in the last 12 months

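### Does the silence on active treatments other than emollients, and on recording treatment use between Day 0 and end of treatment, require a change to the protocol?

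*Protocol*

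**What the plan says.** The opening section of the protocol sets out the groups: "The study involves four groups of patients (patients with psoriasis, atopic dermatitis, eczema and chronic pruritus". All receive the same irradiation, and no control, sham or randomisation is described.

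On other treatment, the paragraph after the visit schedule says "During the treatment patients were allowed to use emollients". Three eligibility criteria come near the subject:

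- Exclusion 8 removes "Patients using medications with proven phototoxic effect".
- Exclusion 4 removes "Patients who participated in another experiment / clinical trial within 30 days prior to inclusion in the experiment".
- Inclusion 6 asks for a patient who "undertakes to strictly follow medical recommendations" and who can meet the protocol's requirements. Exclusion 5 is its mirror image.

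On recording, the Day 0 list says "an interview will be made regarding comorbidities and the treatment used". The paragraph after the schedule adds "At the last control visit (end of treatment visit) the same parameters will be assessed as during the first one". Visits 2 to 6 are one-line entries; Visit 4, for example, reads "evaluation of the effectiveness and safety after 30 sessions of blue light phototherapy", followed by blood sampling. Visit 8 is a check of clinical state four weeks after therapy ends.

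**The concern.** In a single-treatment study judged by change from baseline, nothing in the design separates the device from another active treatment begun during the course. Two safeguards are usual: a rule on what else may be used, and a dated record of what was used. Here the rule is one sentence that can be read as emollients only or as emollients too, and the record is expressly required at only two points.

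If a patient started or intensified an active treatment between those points, the improvement could be counted as an effect of blue light at Visits 2 to 6, at end of treatment, or at Visit 8. A later analysis plan could not date treatment that nobody wrote down when it began.

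**Working it through.** The protocol gives no sample size, effect size or error rate that bears on this point. The check is a comparison of the texts plus simple timing arithmetic.

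**1. Is the rule really open?** No criterion bars active treatment in words. Exclusion 8 concerns phototoxic drugs and exclusion 4 concerns earlier trial participation, so neither settles it. But permission for emollients has little purpose if stronger treatments were open as well. Inclusion 6 and exclusion 5, which bind patients to the study's requirements, lend the restrictive reading some weight. Nothing in the protocol contradicts that reading.

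**2. Does absence from a visit heading mean that the item is not collected?** Two comparisons within the protocol say no.

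| Item | Required by a general sentence | Named in the headings of Visits 2 to 8 |
|---|---|---|
| Photographs | Yes, at every visit | No |
| Treatment use at end of treatment | Yes, through the cross-reference to the first visit | No |

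The headings of Visits 2 to 6 also name no severity scale, although effectiveness cannot be evaluated without one. They are labels, not full lists.

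**3. How long is the interval between the two listed interviews?** Inputs from the opening section and the visit schedule: at most 60 sessions, 3 to 5 per week, an observation period of at most 12 weeks, evaluations every 10 sessions, and Visit 8 at 4 weeks after therapy. Assumptions: little time between Day 0 and the first session, and no pause between cycles.

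- Full course at 5 per week: 60 / 5 = 12 weeks. Visits 2 to 6 (sessions 10, 20, 30, 40, 50) lie between the interviews.
- At 3 per week under the cap: 12 × 3 = 36 sessions. Visits 2 to 4 lie between.
- If the cap also covers Visit 8, which is not stated: 12 − 4 = 8 weeks. That gives 8 × 3 = 24 sessions (Visits 2 and 3 between) or 8 × 5 = 40 sessions (Visits 2 to 4 between).
- Ignoring the cap, 60 sessions at 3 per week would take 60 / 3 = 20 weeks. How the cap fits that schedule is a separate question.
- Asking at every evaluation visit would shorten the interval to 10 / 5 = 2 weeks or 10 / 3 = 3.3 weeks.

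**4. What does the longer interval cost?** For the comparison of Day 0 with end of treatment, the analyst needs to know whether a patient added treatment. An interview at the end that looks back over the course supplies this. The exact date matters only for placing the change before or after a particular interim visit. Patients also attend 3 to 5 times a week, so there are many occasions to note a change, although the protocol does not require a note.

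**5. Which way would a bias run?** Treatment added after Day 0 pushes apparent benefit up. Treatment stopped after Day 0 could push it down. Treatment begun shortly before Day 0 and continued could push it up, but the Day 0 interview already covers that case and later recording would not remove it. No figure in the protocol allows a size for any of these.

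**The case for a change.** The strongest case for a change is that permitted treatment and the content of each visit are protocol matters, which an analysis plan cannot repair afterwards. The restrictive reading of the emollient sentence is an inference. The sentence is also in the past tense, so it reads more like a description than a rule. Nothing in the text requires treatment use to be asked about at Visits 2 to 6 or at Visit 8, no start or stop dates are requested, and the remedy would cost one form item at visits that already take place.

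Part of this stands. The text does not say outright whether the emollient permission is exclusive. Dates taken from the closing interview would rest partly on recall. The 4 weeks before Visit 8 have no listed treatment record at all.

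What does not stand is the step from not listed to not collected, since the protocol's own headings omit items it requires elsewhere. Nor would dated recording solve the underlying problem: without a comparator, natural course and regression to the mean remain mixed with the device effect. How to analyse patients who add treatment, for instance whether to count them as non-responders, is commonly left to an analysis plan, which is not shown here.

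**Conclusion.** No change to the plan follows. This is a gap in detail that investigators and analysts can be expected to fill sensibly: ask about other treatment as part of judging effectiveness and safety, use the closing interview to identify patients who added any, keep them in the analysis, and describe them. The protocol neither contradicts itself on this point nor states a rule or figure shown to give a wrong result.

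The extent of the gap is loss of dating precision over at most about 12 weeks under the stated cap (8 weeks if the cap includes Visit 8), plus 4 weeks before a follow-up visit that the protocol describes only as a check of clinical state. The bias itself cannot be sized.

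The conclusion rests on three assumptions: that the emollient sentence is applied as emollients only, that the closing interview covers the whole course and not just current use, and that the one-line visit headings do not limit what is collected. Whether other active treatment is permitted is a clinical rule for the sponsor to set.

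### Do inclusion items 3 and 4, listed without an 'or', shut out patients or leave those who meet both without lesion scores?

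*Protocol*

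**What the plan says.** The study outline at the start of the protocol states: "The study involves four groups of patients (patients with psoriasis, atopic dermatitis, eczema and chronic pruritus". The Day 0 section then says "Additionally, appropriate scales will be used depending on the disease" and gives one line of scales per condition. The line for the fourth condition is "VAS, 10-item Pruritus Severity Scale – chronic pruritus", with no lesion score.

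The inclusion criteria are six numbered items. Item 3 is "Diagnosis of psoriasis / eczema / atopic dermatitis" and item 4 is "Chronic pruritus (lasting more than 6 weeks". Nothing joins the two, and no introductory sentence says whether all items must be met. Exclusion item 6 removes "Patients with skin diseases other than inflammatory skin diseases or chronic pruritus".

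For the end of treatment visit, the paragraph on follow-up visits says that "the same parameters will be assessed as during the first one". No sentence says which group a patient enters who has one of the three diagnoses and also itch of more than 6 weeks.

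**The concern.** The other four inclusion items (consent, age, general health, ability to comply) apply to every patient; item 1, for instance, is "Informed consent to participate in a medical experiment". In such a list, items 3 and 4 look like two further conditions that everyone must meet. A patient with chronic itch and none of the three diagnoses would then be ineligible and the fourth group would have no patients of its own. A patient with psoriasis and no long-standing itch would be turned away as well.

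The second worry survives even if the items are alternatives. A patient with a listed diagnosis and more than 6 weeks of itch fits two groups. If that patient were entered under chronic pruritus and scored only on that line, PASI and PGA, IGA, or SCORAD and EASI would not be recorded at Day 0, and the end of treatment visit would repeat the same short set. A baseline score that was not taken cannot be recovered later.

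**Working it through.** The protocol gives no figure to reproduce on this point. The check compares the sections with one another.

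**Step 1: what each reading admits.** Let D be a listed diagnosis and P be itch lasting more than 6 weeks.

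| Profile | Both required (D and P) | Alternatives (D or P) |
|---|---|---|
| D and P | admitted | admitted |
| D only | refused | admitted |
| P only | refused | admitted |
| neither | refused | refused |

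The first reading admits 1 of 4 profiles and the second 3 of 4; they differ on 3 − 1 = 2. These are logical cells, not patients. The protocol does not give the share of patients in each cell, so the counts do not measure an effect.

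**Step 2: which reading fits the rest of the protocol.**
- Under the first reading nobody with P only is admitted, so a separate pruritus group would make no sense. The study outline names one.
- The Day 0 section gives that group its own scale line.
- Exclusion item 6 joins inflammatory skin diseases and chronic pruritus with 'or'.
- The inclusion list does not itself say that every item must be met.

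Only the either/or reading is consistent with all of these.

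**Step 3: what a patient who meets both would have measured.** Scales on the Day 0 lines:

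| Line | Lesion or global scores | Itch scales | Total |
|---|---|---|---|
| Psoriasis | PASI, PGA (2) | VAS, 10-item scale (2) | 4 |
| Eczema | IGA (1) | VAS, 10-item scale (2) | 3 |
| Atopic dermatitis | SCORAD, EASI (2) | VAS, 10-item scale (2) | 4 |
| Chronic pruritus | none (0) | VAS, 10-item scale (2) | 2 |

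The pruritus set is contained in each of the other three. A patient who fits the pruritus line and a diagnosis line therefore gets everything on both by following the diagnosis line; the two lines never compete. The selector in the text is the disease, not a group label. A patient with psoriasis and long-standing itch has psoriasis, so that line applies whichever group the patient is counted in. The end of treatment visit repeats the Day 0 set and so inherits the full set.

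**Step 4: what else the group label could alter.** The protocol describes no randomisation and no group-specific treatment. The irradiation schedule and Visits 1 to 8 are common to all. Skin examination with photographs at Day 0, photographs at each visit and the re-evaluation of the skin at Visit 7 also apply to everyone. The label changes neither exposure nor visits.

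**The case for a change.** The best argument for a change is that the inclusion list is what a site applies at screening, and its meaning should not have to be pieced together from other sections. Item 3 marks its own alternatives with slashes, yet nothing marks item 4 as an alternative to item 3. Item 4 also does not restrict itself to itch without a skin diagnosis, and the itch scales on all three diagnosis lines show that overlap is expected. Eligibility and baseline scoring are protocol matters that a later analysis plan could not repair, and one connector and one sentence would cost almost nothing.

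Part of this stands. The connector is missing, and no rule says where a patient meeting both is counted. The harm does not stand. Losing a lesion score would require staff to set aside a known diagnosis and the instruction to choose scales by disease. The itch scales on the diagnosis lines in fact suggest that itch accompanying a diagnosis is handled within that diagnosis, leaving the pruritus group for patients without one. How a patient with two qualifying conditions is counted in the summaries is ordinary analysis-plan content, and that plan may exist without being shown here. Low cost does not justify a change when no result improves.

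**Conclusion.** No change to the plan follows. The missing connector is a clerical slip that the study outline, the Day 0 scale lines and exclusion item 6 resolve in one direction, so adding it would alter nobody's eligibility in practice. The unwritten assignment rule is a gap that staff and analysts would fill sensibly by letting a known diagnosis decide. The 2 of 4 profiles on which the readings differ arise only by entertaining a reading that the rest of the protocol rules out.

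This rests on two assumptions: that staff choose scales by the patient's disease, as the Day 0 section says, and that the counting of patients with two qualifying conditions is settled at the analysis stage. The share of patients meeting both items is not stated, and the conclusion does not depend on it, because the measurement sets are nested and treatment is common to all. Nothing in the protocol suggests that eligible patients were refused.
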